**REVISION HISTORY**

| Revision # | Version Date | Summary of Changes | Consent Change? |
|-------------------|---------------------|---------------------------|------------------------|
|                   |                     |                           |                        |
|                   |                     |                           |                        |
|                   |                     |                           |                        |
|                   |                     |                           |                        |
|                   |                     |                           |                        |

## 1.0 Study Summary

| Protocol Information                               | Description   |
|---|--|
| Study Title  | Decreasing Alzheimer's Risk through Online Choreographed Exercise (DANCE) – Down Syndrome  |
| Study Design                                       | Single Arm Pilot Feasibility Trial   |
| Primary Objective                                  | To assess the feasibility of a 12 week remotely delivered group dance intervention.  |
| Secondary Objective(s)                             | 
 
1. To assess changes in aerobic fitness and cognitive function in response to a 12 week remotely delivered group dance intervention.
 
2. To assess the intensity and total energy expenditure of remotely delivered group dance sessions
 
 |
| Research Intervention(s)/ Investigational Agent(s) | Adults with Down syndrome (n=20) will participate in a 12 week, remotely delivered choreographed exercise intervention. Classes will take place 2 times per week and be 35 minutes in length.  |
| IND/IDE #  | NA   |
| Study Population                                   | Adults (age 18-64) with Down syndrome  |
| Sample Size  | 20   |
| Study Duration for individual participants         | 12 Weeks   |
| Study Specific Abbreviations/ Definitions          | AD, Alzheimer's Disease; DS, Down syndrome; ID, intellectual disability; MVPA, moderate-to-vigorous physical activity  |

## 2.0 Objectives

2.1 Adults with Down syndrome (n=20) will participate in a 12 week, remotely delivered choreographed exercise intervention. Classes will take place 2 times per week and be 35 minutes in length. Prior to the start of the intervention (baseline) and at the conclusion of the intervention (week 12), aerobic fitness (6-minute walk test), cognitive function (modified cued recall), and physical activity enjoyment will be assessed. Attendance, retention, and adverse events will be collected on an ongoing basis throughout the intervention. The purpose of this pilot project is to assess the usability, feasibility, and preliminary effectiveness of a remotely delivered choreographed exercise intervention for the prevention of Alzheimer's disease in adults with Down syndrome. This project will address the following aims:

- Aim 1: Assess the feasibility of a 12 week, remotely delivered group dance intervention
- Aim 2: Assess changes in aerobic fitness and cognitive function in response to a 12 week remotely delivered group dance intervention
- Aim 3: Assess the intensity and total energy expenditure of remotely delivered group dance sessions

2.2 We hypothesize the following:

- Aim 1: Session attendance and participant retention will be  $\geq 80\%$ , and physical activity enjoyment (measured using the Physical Activity Enjoyment Disabilities Scale) will increase from baseline to week 12
- Aim 2: We expected significant improvements in aerobic fitness and cognitive function across the 12 week intervention
- Aim 3: Energy expenditure will exceed  $\geq 3.0$  METs during the exercise sessions and average heart rate will reach 65 % of age-estimated maximal heart rate

## 3.0 Background

Down syndrome (DS) or trisomy 21 is the most common chromosomal abnormality associated with an intellectual disability (ID) [1]. The current incidence of DS is 1 in every 650 live births [2, 3] which is ~30% higher than in 1979, largely due to women conceiving after age 35 [4]. Consequently, the prevalence of DS in the U.S. increased from an estimated 49,923 in 1950 to ~250,700 individuals in 2017 [3, 5]. The life expectancy for individuals with DS has increased dramatically in recent decades from 4 yrs. in the 1970's due to high rates of congenital heart defects, to 60 yrs. currently [6]. Alzheimer's disease (AD) is currently the leading cause of death in individuals with DS. All adults with DS will develop pathology related with Alzheimer's disease (AD) [4, 7, 8]. The median age of dementia onset is 53.8 years [9], and the lifetime incidence is 90% [8, 10].

For adults without DS, increased moderate-to-vigorous physical activity (MVPA) during mid-life [11-14] and older adulthood [15-17] may be effective in maintaining or improving components of cognition, including attention, memory, and executive function.

MVPA obtained through structured exercise appears to have the greatest benefit on cognition [18-20]. The limited research in adults with DS suggests that MVPA is closely associated with cognition [21, 22]. For example, Fleming et al. [21] reported that percent of time spent in MVPA was significantly correlated with 8/9 cognitive outcomes used the ABC-DS cognitive battery [23]. Similarly, a study by Pape et al. [22] which followed 214 participants across 12 months, observed that higher MVPA at baseline was associated with a 62% reduced risk of decline in memory and orientation at 12 months. Additionally, previous intervention studies in adults with DS have demonstrated the potential for acute or short-term ( $\leq 12$  wks.) exercise to improve cognitive outcomes [24-28]. For example, Chen et al [29] compared the response of 3 components of executive function (choice-response time, attention shifting and inhibition) to an acute bout of moderate intensity exercise (20 min treadmill walk,  $n=10$ ) with an attentional control (20 min video,  $n=10$ ) in adults with DS. Compared to the control group, participants in the exercise group had non-significant improvements in choice-response time ( $p = 0.32$ ) and attention shifting ( $p = 0.13$ ). Participants in the exercise group had statistically significant improvement in inhibition compared with control ( $p = 0.03$ ).

While MVPA might serve to benefit those with DS, it is estimated that only 9% of adults with ID, including those with DS, [30] achieve 150 minutes per week of MVPA as recommend by the Physical Activity Guidelines for Americans [31] compared with ~52% of typically developed adults [32]. Adults with DS face unique barriers to participation in MVPA including disinterest or inability to participate in typical exercise modes, e.g., walking, jogging etc., challenges with gait and/or coordination, lack of access to adapted options for MVPA, and lack of social support and low self-efficacy for exercise [33, 34]. Previous research [35]/observations by our group and others suggests that dance activities are a preferred form of exercise for adults with DS. Dance, which is characterized by rhythmic physical movements offers the potential for social engagement, and stimulation of brain functions including attention, memory, executive function, and visuospatial processing that are commonly affected by aging and cognitive decline [36, 37], particularly in individuals with DS. However, empirical evidence to support the feasibility of a remotely delivered group dance intervention and evaluation of the intensity and energy expenditure achieved by a dance intervention for adults with DS are currently unavailable and will be the focus of the proposed pilot trial.

## **4.0 Study Endpoints**

- 4.1 The primary study endpoint is at the conclusion of the 12 week intervention. A secondary endpoint is upon participant withdrawal.
- 4.2 Participants will be removed from the study due to safety concerns if any arise.

## **5.0 Study Intervention/Investigational Agent**

Adults with DS ( $n=20$ , age = 18 to 64 yrs.) will be asked to attend 35 min. remotely delivered (Zoom®) group dance sessions twice weekly across 12 weeks. All sessions will be directed by an instructor experienced in leading 35 min, group remote exercise sessions for individuals with intellectual disability as part of the ongoing exercise program for individuals with intellectual disability offered by the Division for Physical Activity and Weight Management. Classes will include a 5-minute warm up, 25 minutes of exercise designed to target moderate intensity activity, and a 5 minute cool down. During the 25 minutes of exercise, approximately 15 minutes of this section will be used to complete “floor progressions”. In a traditional dance class, “floor progressions” are

used to practice fundamental dance skills while traveling across the floor, such as marching across the floor to the beat of the music, side shuffle across the floor, or step-kicks across the floor. Participants will be asked to do this style of movement in place or within a radius where they can move safely in their homes and stay within range of the video camera so that exercise instructors can ensure participant safety. The final 10 minutes of the 25-minute exercise block will be used to teach dance moves as a part of a choreographed exercise routine which will be learned over the course of 12 weeks. Participants will start this section by practicing parts of the dance learned in a previous session or by learning new sections of the dance. Types of moves used in this dance routine will be similar to those used in the “floor progression” segment, including marching to the beat for an 8-count of music, stepping and clapping for an 8-count of music, swaying arms while stepping side to side for an 8-count. The choreographed dance will be designed by an individual experienced with teaching dance to adults with intellectual disabilities to ensure it is level appropriate. Each week, participants will learn 1-2 new dance moves as a part of the choreographed dance and practice these moves with the music assigned to the dance with the instructor as a part of class.

## 6.0 Procedures Involved

- 6.1 This is a 12-week pilot intervention for 20 adults with Down syndrome. The intervention will include a 2x weekly choreographed exercise intervention led by staff trained to deliver exercise interventions in this population. The structure of the class will be similar to that used in the ongoing remote exercise program for individuals with intellectual disability offered by the Division for Physical Activity and Weight Management, but substituting choreographed exercise (dance) movements to replace the aerobic component of this program. Participants will be asked to attend 2x weekly group classes remotely using Zoom® video conferencing (San Jose, CA). All outcomes will be assessed by research assistants at baseline and week 12, with the exception of the energy expenditure assessment and weekly class attendance. Outcome assessments will take place at the University of Kansas Medical Center, in Kansas City, KS. Intervention classes will take place in participant homes, using self-provided devices.
- 6.2 All assessments will be completed by appropriately trained staff with experience conducting assessments in adults with Down syndrome.
- 6.3 Anthropometrics. Research staff will measure weight, height, waist circumference, and hip circumference. Weight will be measured on a calibrated scale to the nearest 0.1 kg. Standing height will be measured with a stadiometer. BMI will be calculated as weight (kg)/height (m^2). Waist and hip circumference will be assessed using standard procedures such as those described by Lohman et al. [38]. Two measurements will be obtained with the outcome recorded as the average of the closest 2 measures. Blood Pressure and Heart Rate will also be collected following a period of seated rest (≥5 minutes).
- 6.4 Demographics. Basic demographic information including age, date of birth, race, ethnicity, sex, gender identity, and a brief health history will be collected at the baseline assessment.
- 6.5 Aerobic fitness. Aerobic fitness will be assessed using the 6-minute walk test [39-41] at baseline and week 12. Participants will be asked to

continuously walk along a pre-measured walking course for a total of six minutes. Participants are free to self-select pace of this walk and take breaks as needed. The total distance covered in the allotted time will be recorded.

- 6.6 Cognitive function. The Modified Cued Recall Test (mCRT)[42] will be used to assess cognitive function. The mCRT is used to assess episodic memory, and is a version specifically modified for individuals with DS. During this assessment, participants are asked to recall 12 objects previously shown to them using a set of cards following a learning phase. Participants are given one minute to freely recall these items before receiving category-based cues to retrieve remaining items. Participants are asked to complete this for a total of three trials and the total number of items across all three trials is summed.
- 6.7 Energy Expenditure of Remote Exercise Sessions. Energy expenditure of the remote sessions will be assessed using a previously validated portable, open-circuit indirect calorimeter (Cosmed, Italy) which measures breath-by-breath ventilation, expired oxygen, and carbon dioxide. The flow turbine will be calibrated using a 3.0-L syringe. The lightweight (~1.5 kg) portable system will be attached by a harness around the waist and shoulders of the participant before each assessment. During exercise sessions, participants will breathe into a facemask that directs air into the unit housing the O2 and CO2 analyzers. Data will be retrieved for analysis via a serial port interface and software provided with the calorimeter and aggregated over 20-second epochs for the calculation of 1-min averages. MET levels will be age corrected using the Schofield equation as recommended by McMurray et al.[43]. Participants will also be provided with a FitBit device to measure heart rate achieved during the exercise sessions. Exercise instructors will remind participants to start and stop devices at the beginning and end of each exercise session. Device data will be shared with research staff.
- 6.8 Attendance at remote exercise sessions. After each session, the interventionist will record attendance. Overall attendance will be expressed as the percentage of possible sessions attended.
- 6.9 Physical Activity Enjoyment. Physical activity enjoyment will be assessed at baseline and week 12 of the intervention using the Physical Activity Enjoyment Scale [44]. Exercise self-efficacy will also be assessed at baseline and week 12. Self-efficacy will be assessed using the Self-Efficacy for Activity for Persons with Intellectual Disabilities Scale [45]. Finally, participants will complete a survey of intervention implementation success (acceptability, appropriateness, feasibility) assessed using validated 5-point Likert scales [46] at week 12 of the intervention. Participants will complete these surveys via REDCap.

## **7.0 Data and Specimen Banking NA**

## **8.0 Sharing of Results with Subjects**

- 8.1 Study results will not be shared with participants.

## **9.0 Study Timelines**

- 9.1 The intervention will last for 12 weeks. Baseline testing visits will occur within two weeks of the start of the intervention and week 12 visits will occur within 2 weeks of the program ending. Based on these parameters, study enrollment will last up to 16 weeks including pre, and post intervention testing.
- 9.2 Participants will be recruited in two cohorts of 10 participants each. It is projected for the first cohort to begin in the Fall of 2024, with recruitment taking place in summer and early fall. The second cohort will begin in early 2025, with ongoing recruitment efforts starting during the delivery of the intervention to the first cohort.
- 9.3 Primary analyses will be completed in Summer 2025, following the conclusion of the second cohort. This will allow ample time for data collection and processing from both cohorts.

## **10.0 Inclusion and Exclusion Criteria**

- 10.1 First, interested participants will complete a web-based initial eligibility questionnaire using REDCap, where they will provide the age, sex, race, and answer questions related to inclusion/exclusion. Those deemed potentially eligible will be contacted for a phone screen to determine final eligibility and discuss informed consent.
- 10.2 Remote video chat sessions (Zoom) or a phone call will be scheduled with participants and their legal guardian (if applicable) deemed to be initially eligible. During this call, the research study will be explained to participants and their legal guardian (if applicable) and eligibility criteria will be assessed.
- 10.3 *Inclusion criteria:* 1) Age 18-64 yrs. with a diagnosis of Down syndrome. 2) Sufficient functional ability to communicate through spoken language.3) No plans to relocate outside the study area over the next 12 weeks 4) Possession of a personal device that allows for connectivity to the internet and participate in 2x weekly group video calls. 5) Ability to participate in moderate intensity physical activity
- 10.4 *Exclusion criteria:* 1) Serious medical risk (e.g., cancer, recent heart attack, stroke, pregnancy, angioplasty as determined by the research staff. 2) unwilling to participate in outcomes assessments 3) uninterested

## **11.0 Vulnerable Populations**

- 11.1 Study procedures will be explained in an appropriate manner by Staff familiar in working with adults with Down syndrome. Adequate time will be given for questions and consideration by both the potential participant and a caregiver.

## **12.0 Local Number of Subjects**

- 12.1 A total of 20 participants will be recruited to join the study, across two cohorts of 10 participants.

## **13.0 Recruitment Methods**

- 13.1 The recruitment plan was informed by our experience with completed projects where we successfully recruited adults with DS [47-49]. As in our previous trials, project staff will contact local community agencies serving adults with DS, case managers, and CDDOs by mail or email, provide presentations at CDDO meetings, and text for CDDO newsletters describing the project. Interested adults with DS or their parent/caregiver will be asked to contact the study coordinator via email or a dedicated toll-free study phone number that will be included in all recruitment materials. Participants will complete a basic eligibility survey using REDCap. The study coordinator will then contact those deemed eligible by phone to answer questions and conduct and ensure eligibility. Zoom® meetings will be scheduled with those remaining interested and potentially eligible to complete eligibility screening and to obtain informed consent or parent/guardian consent and participant assent in cases where the participant has a surrogate decision maker.
- 13.2 A flyer will be sent to all parties listed above and used for recruitment purposes. This flyer will include basic study information and contact information for research staff. A copy of the flyer is attached.

## **14.0 Withdrawal of Subjects**

- 14.1 Participants will be withdrawn from the research without their consent if an SAE occurs which is deemed by the study team and PI and unsafe for continued participation.
- 14.2 Upon withdrawal from the study, all research activities will cease, and no additional data will be collected. Participants will no longer be able to attend the weekly exercise classes.

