## **18.0 Provisions to Monitor the Data to Ensure the Safety of Subjects**

18.1 An adverse event (AE) is any unfavorable medical occurrence in a human subject participant including any abnormal sign, symptom, or disease that is temporally associated with the participants' involvement in the research even if it is not considered related to the participation in the study. Signs and symptoms that are consistent with normal exercise including work-related dyspnea, fatigue, sweating, or light soreness of muscles will not be considered AEs. A serious adverse event (SAE) is defined as any adverse event that results in death, a life-threatening event, inpatient hospitalization, or a permanent disability.

AEs and SAEs will be tracked by the research assistant, study coordinator, or principal investigator for each exercise session. These events will be tracked on an adverse event form in REDCap and will include any events that occurred during or after the exercise sessions. Each reported event will be documented if it meets the criteria for an AE or SAE. Documentation will include a description of the event, when and how it happened, and any documentation to determine event severity and relatedness to the research study. Follow-up for each occurrence will be initiated by the study team and continued until the event is resolved. The principal investigator for the study will review and evaluate adverse events within 72 hours and a summary of these events can be provided to the IRB on an annual basis. Deaths will be reported within 24 hours and unanticipated SAEs will be reported within 48 hours to the IRB. All other SAEs will be reported semi-annually.

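### Protocol 14.2 stops all data collection at withdrawal, while 18.1 requires each adverse event to be followed until resolved; nothing says which rule governs an event still open at a safety withdrawal

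*Protocol*

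**What the plan says.** Section 14 of the protocol has two parts. Under 14.1 the study team withdraws a participant, without needing that person's consent, "if an SAE occurs which is deemed by the study team and PI and unsafe for continued participation". Section 14.2 gives the consequence: "Upon withdrawal from the study, all research activities will cease, and no additional data will be collected". A further sentence in 14.2 ends access to the classes. Section 4.2 separately provides for removal on safety grounds.

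Section 18.1 sets the duty for adverse events: "Follow-up for each occurrence will be initiated by the study team and continued until the event is resolved". The record is kept on an adverse event form in REDCap and is to include "any documentation to determine event severity and relatedness to the research study". Serious events are defined as "any adverse event that results in death, a life-threatening event, inpatient hospitalization, or a permanent disability". Nothing in 18.1 limits the duty to people who are still enrolled.

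The SAP mentions neither adverse events nor withdrawal.

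**The concern.** The only withdrawal rule written out in section 14 is triggered by a serious adverse event. The stop on data collection in 14.2 therefore applies directly to participants whose event has just ended their participation, and some of those events will not be over on the day of withdrawal. Staff handling a withdrawal would naturally turn to section 14, which tells them to collect nothing more. Staff handling the event would turn to section 18, which tells them to continue.

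What is at stake is the completeness of one kind of record: how the event ended, how severe it finally was, and whether it was finally judged related to the intervention. In a pilot of 20 people meant to inform later studies, an incomplete record of even one such event would be a noticeable gap in the safety description.

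**Working it through.** No formula applies, because the point depends on no sample size, error rate or event count. The check is whether the two rules can both be kept in each situation that can arise.

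| Situation | 14.2 | 18.1 | Compatible? |
|---|---|---|---|
| Event open, participant stays in the study | Not triggered | Follow until resolved | Yes |
| Event resolved and documented before withdrawal | Stop data collection | Nothing left to follow | Yes |
| Withdrawal with no adverse event | Stop data collection | Not triggered | Yes |
| Event open on the day of withdrawal | Stop data collection | Follow until resolved and document | No |

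Only the last row conflicts. Three questions decide whether the text removes that conflict.

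1. **Does 14.2 cover adverse event data?** Its first sentence stops research activities and data collection in general; class attendance is dealt with in a separate sentence. Section 2.1 includes adverse events in what the study collects: "Attendance, retention, and adverse events will be collected on an ongoing basis throughout the intervention". Section 18.1 puts them on a REDCap form, and 17.2 makes REDCap the study's data management system. On its plain wording, 14.2 covers them.

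2. **Does 18.1 end at withdrawal?** No. It applies to each occurrence and ends at resolution.

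3. **Does anything else set an order of precedence?** No. The rest of section 18 adds reviews and reporting duties but does not mention withdrawn participants. Section 4.1 names withdrawal as a secondary endpoint but provides no safety follow-up after it. The SAP is silent.

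The last row is not remote from the protocol's own thinking. Section 18 names cardiovascular events and muscle or joint injuries as the main risks, and such events need not be over by the time a participant is withdrawn.

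**The case against.** The strongest reply is that 18.1 is the specific safety rule and 14.2 the general one. On that reading, outcome assessments and classes stop at withdrawal while the duty to follow a known event continues. Section 2.1 speaks of collection during the intervention, so it does not settle what happens afterwards. This is probably what was intended, and it limits the seriousness of the point. It does not remove the point, because 14.2 is equally specific about withdrawal and the protocol nowhere states the order of precedence.

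The consent pages were not available for this review and may contain wording on contact after withdrawal. One should therefore not conclude that staff or participants had no instruction. Such wording would still leave 14.2 and 18.1 unreconciled within the protocol.

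A reader might infer larger consequences, which the documents do not support:

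- **Late reporting.** Section 18.1 says "All other SAEs will be reported semi-annually" for serious events other than deaths and unanticipated ones, which could suggest a lag of months. But section 18 also makes the principal investigator responsible for reporting serious events to the IRB immediately. A long delay cannot be read from the first sentence alone.
- **A record that closes within days.** Section 18.1 says "The principal investigator for the study will review and evaluate adverse events within 72 hours", but it does not say when that period starts or that withdrawal is decided then. No length of record follows.
- **Distorted adverse event rates.** The monthly review in section 18 concerns rates. An event enters a rate when it occurs, whether or not its resolution is later recorded.
- **A likelihood taken from the definition of a serious event.** Most of the listed outcomes can occur in a living participant, but counting items in a definition says nothing about how often they happen.

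**Conclusion.** The conflict is real but minor. For a participant withdrawn under 14.1 or removed under 4.2 with an event still open, 14.2 and 18.1 give opposite instructions, and the protocol does not say which governs. If 14.2 is followed, the resolution and the final severity and relatedness of that event may be missing. The event is still counted and reported. Attendance, retention, the fitness and cognitive comparisons and the energy expenditure results are untouched, and no stated figure changes.

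No probability is attached, because the documents give no rate of serious events, of safety withdrawals or of events open at withdrawal. If no such case occurred, nothing was lost. The conclusion rests on reading 14.2 literally; if the team in practice treated 18.1 as overriding, only the wording is at fault. It would be wrong to infer that safety follow-up is absent from the plan: 18.1 requires it, and the defect is that 14.2 contradicts it.

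**What to change.** Add an exception to the data-collection sentence in 14.2, for example: *except that any AE or SAE open at withdrawal will be followed and recorded on the REDCap adverse event form until resolved or stable, as in 18.1, unless the participant or guardian declines.* The words *or stable* are needed because a permanent disability may never resolve. Sections 14.1 and 4.2 and the SAP's retention definition can stay as they are.

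The SAP is dated November 2025 and written in the past tense, so conduct may well be complete. In that case an amendment would change little. The report should instead state whether any participant was withdrawn for safety and, if so, whether the event was followed to resolution.

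The cost is one sentence in the protocol or one in the report. The form already exists, and no visit or outcome assessment is added.
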